13.2 Sample Size, Accrual Rate and Study Duration

The target sample size for this study is 54 patients. We plan to enroll a total of 60 patients to account for screen failure, resting HR < 80 at baseline visit, withdrawals, or loss to follow up. Based on our clinical volume, we plan to recruit 2-3 patients per month over a cumulative accrual period of 24-36 months. Each patient will be followed for the 6 week duration of the study. There is no long-term follow-up planned in this study.

Accrual Targets					
Ethnic Category	Sex/Gender				
	Females		Males		Total
Hispanic or Latino	3	+	4	=	7
Not Hispanic or Latino	24	+	29	=	53

Ethnic Category: Total of all subjects	27	(A1)	+	33	(B1)	=	60	(C1)
Racial Category								
American Indian or Alaskan Native	1		+	1		=	2	
Asian	1		+	1		=	2	
Black or African American	3		+	4		=	7	
Native Hawaiian or other Pacific Islander	1		+	1		=	2	
White	21		+	26		=	47	
Racial Category: Total of all subjects	27	(A2)	+	33	(B2)	=	60	(C2)

(A1 = A2)

(B1 = B2)

(C1 = C2)

13.3 Stratification Factors

All patients will first be stratified into two groups according to pre-randomization treatment with beta-blocking agents. Patients within each beta-blocker group will then undergo four way randomization using permuted blocks, dividing the two strata into four groups each: ivabradine with sophisticated autonomic testing, placebo with sophisticated autonomic testing, ivabradine with no sophisticated autonomic testing, placebo with no sophisticated autonomic testing. These four groups will be created in a 1:1:1:1 ratio. Randomization will be performed by the ODQ at Dana Farber Cancer Institute.

Monitoring and efficacy determination will not be done separately for the different strata. An ANCOVA model (for normally distributed data) adjusting for the stratification factors (beta blocking agents [Yes, No], autonomic function testing [Yes, No]) or Quade test adjusting for the stratification factors (beta blocking agents [Yes, No], autonomic function testing [Yes, No]) (for non-normally distributed data) will be implemented to compare the change in various endpoint with ivabradine versus placebo.

13.4 Interim Monitoring Plan

Patients will be enrolled continuously in this trial over the course of the trial. Each patient will be followed for the 6 week duration of the study. There are no formal interim monitoring plans in this trial. However, data will be submitted to the DFCI DSMB every 6 months and the recommendations of the DSMB regarding trial continuation will be followed accordingly.

13.5 Analysis of Primary Endpoint

The primary end-point of this study is the change in resting HR with ivabradine, compared to placebo, in survivors of lymphoma with mediastinal involvement who were treated with mediastinal/mantle radiation and have a resting HR \geq 80 bpm.

We will calculate the change in resting HR (from EKGs) from baseline to 6 weeks for each patient in the study (n=60). An ANCOVA model (for normally distributed data) adjusting for the stratification factors (beta blocking agents [Yes, No], autonomic function testing [Yes, No]) or Quade test adjusting for the stratification factors (beta blocking agents [Yes, No], autonomic function testing [Yes, No]) (for non-normally distributed data) will be implemented to compare the change in resting HR with ivabradine versus placebo. A p value < 0.05 using a two-sided test will be considered statistically significant.

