5.2 Pre-Treatment Criteria

5.2.1 Screening Visit: After written informed consent is obtained, we will:

- a) Obtain a detailed history and physical examination
- b) Obtain an EKG to make sure that patients meet eligibility criteria i.e. are in sinus rhythm, have a resting HR \geq 80 bpm, and do not have evidence of high grade AV block.
- c) Review laboratory values obtained within the last 12 months for liver and renal function as described in the inclusion/exclusion criteria.

5.2.2 Baseline Visit: In addition to a detailed history and physical examination, we will:

- a) Obtain an EKG to make sure that patients are in sinus rhythm, have a resting HR \geq 80 bpm, and do not have evidence of high grade AV block prior to study drug randomization.
- b) Obtain a urine pregnancy test to ensure that women of child-bearing age are not pregnant prior to study drug randomization.

5.2.3 2 week visit: In addition to a detailed history to review side effects from study drug treatment, we will:

- a) Obtain an EKG to assess heart rate to determine dose adjustment as stated in section 5.1.

5.2.4 6 week visit: In addition to study procedures outlined below, we will:

- a) Obtain a pregnancy test to ensure that women of child bearing age are not pregnant.

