5.3.1 CTEP and/or CIP IND Agent(s), or other IND agent: N/A

5.3.2 Other Agent(s): N/A

5.3.3 Other Modality(ies) or Procedures

All patients will have a standard 12 lead EKG performed at the screening, baseline, 2 week and 6 week visits.

All patients will undergo exercise treadmill testing at the baseline and 6 week visits.

All patients will have a 24 hour ambulatory Holter monitor placed at the baseline and 6 week visits.

All patients will complete the SF-36 quality of life questionnaire at the baseline and 6 week visits.

Due to cost constraints, a subset of patients (n=30) will undergo further sophisticated autonomic function testing at the baseline and 6 week visits. Depending on scheduling limitations, they may have to return for a second day at each of these visits to complete the additional autonomic function tests.

a) Exercise treadmill testing

All exercise stress tests will be performed in the cardiovascular stress testing laboratory at Brigham and Women's Hospital by trained exercise physiologists under the supervision of a staff

cardiologist. Patients will avoid consumption of all caffeine containing products for 24 hours prior to exercise treadmill testing. All patients will undergo exercise treadmill testing using a symptom-limited Bruce protocol according to established guidelines.¹⁸ Exercise will be continued until one or more of the following endpoints: exhaustion, symptom limitation, $\geq 85\%$ of age-predicted maximal HR, ≥ 10 mmHg drop in systolic blood pressure (SBP) from baseline, sustained ventricular tachycardia, ST-segment depression ≥ 3 mm measured 80 msec after the J junction, or ST-segment elevation of ≥ 1 mm.

b) 24 Hour Ambulatory Holter Monitor

All patients will have a 24 hour ambulatory Holter monitor placed at baseline prior to study drug initiation and at the 6 week time point, prior to study drug termination. Holter monitors will be placed by the cardiology department at Brigham and Women's Hospital. Patients will be asked to return the Holter monitor in person or via mail to Brigham and Women's Hospital.

c) SF-36 Quality of Life Questionnaire

All patients will be asked to complete short form 36 (SF-36) quality of life healthcare questionnaires at the baseline and 6 week visits.

d) Sophisticated autonomic function testing

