8.2 IND Agent #2: N/A

8.3 Other Agent #1: N/A

8.4 Other Agent #2: N/A

9. BIOMARKER, CORRELATIVE, AND SPECIAL STUDIES

9.1 Biomarker Studies: N/A

9.2 For IDE Protocols Only: Investigational Device Information: N/A

9.3 Laboratory Correlative Studies: N/A

9.4 Other Agent #2: N/A

10. STUDY CALENDAR

Baseline evaluations/tests are to be conducted within 1 week prior to start of protocol therapy. In the event that the participant's condition is deteriorating, laboratory evaluations should be repeated within 48 hours prior to initiation of therapy.

2 week study evaluations and drug up-titration should be administered within ± 3 days of the protocol-specified date, unless otherwise noted.

Week 6 study evaluations/tests should be conducted within ± 7 days of the protocol-specified date and should be completed prior to termination of study drug.

	Screening visit	Baseline	Week 2	Week 6
Agents:		Ivabradine vs. placebo	Ivabradine or placebo dose titration	Study End
Informed consent	X			
Demographics	X			
Medical history	X		X	X
Physical exam		X	X	X
Concurrent Meds	X	X	X	X
Vital signs	X	X	X	X
Height		X		X
Weight		X		X
Serum chemistry ^a	X			
EKG (as indicated)	X	X	X	X
B-HCG		X ^b		X ^b
Exercise stress test		X		X
24-hr ambulatory Holter monitor		X		X
SF-36 QOL questionnaire		X		X
Sophisticated autonomic function testing ^c		X		X
Adverse event evaluation		X-----X		
a: Review of SGOT [AST], SGPT [ALT], creatinine obtained within the last 12 months. b: Urine pregnancy test (women of childbearing potential). c: For subset of patients randomized to receive autonomic function testing				

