11. MEASUREMENT OF EFFECT

11.1 Antitumor Effect- Solid Tumors: N/A

11.2 Antitumor Effect- Hematologic Tumors: N/A

11.3 Other Response Parameters

Primary end point:

1. Change in HR from baseline to 6 weeks with ivabradine vs. placebo.¹⁷

Secondary end point:

1. Change in exercise duration from baseline to 6 weeks with ivabradine vs. placebo.²³

Exploratory end points:

1. Change in markers of additional cardiac autonomic function: respiratory sinus arrhythmia amplitude, Valsalva ratio, heart rate variability, cardiovagal CASS and adrenergic CASS from baseline to 6 weeks.¹⁹
2. Change in patient reported quality of life (as assessed using then SF 36 questionnaire) from baseline to 6 weeks with ivabradine compared to placebo.²⁴

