13.6 Analysis of Secondary Endpoints

The secondary end-point of this study is the change in exercise duration with ivabradine, compared to placebo, in survivors of lymphoma with mediastinal involvement who were treated with mediastinal/mantle radiation and have a resting HR \geq 80 bpm.

We will calculate the change in exercise duration (from exercise treadmill stress tests) from baseline to 6 weeks for each patient in the study (n=60). An ANCOVA model (for normally distributed data) adjusting for the stratification factors (beta blocking agents [Yes, No], autonomic function testing [Yes, No]) or Quade test adjusting for the stratification factors (beta blocking agents [Yes, No], autonomic function testing [Yes, No]) (for non-normally distributed data) will be implemented to compare the change in exercise duration with ivabradine versus placebo.

We will then repeat the analysis with change in resting HR as an additional independent variable to assess whether change in resting HR affects exercise duration. A p value < 0.05 using a two-sided test will be considered statistically significant.

Exploratory end-points of this study are:

- 1) Change in additional markers of cardiac sympatho-vagal balance with ivabradine, compared to placebo, in survivors of lymphoma with mediastinal involvement who were treated with mediastinal/mantle radiation and have a resting HR \geq 80 bpm.

Since this is an exploratory end-point and due to cost constraints, it will only be conducted in half the patients enrolled in the trial (n=30) and no power calculation has been made. The cardiovagal composite autonomic severity score (CASS) and adrenergic CASS will be calculated at baseline and at 6 weeks (as described in Section 5.3.3) for each patient in this substudy. The change in CASS and adrenergic CASS will then be assessed for each patient. Quade test adjusting for the stratification factors (beta blocking agents [Yes, No], autonomic function testing [Yes, No]) (for ordinal data) will be implemented to compare the change in CASS and adrenergic CASS in patients treated with ivabradine versus placebo. A p value < 0.05 using a two-sided test will be considered statistically significant.

- 2) Change in health related quality of life with with ivabradine, compared to placebo, in survivors of lymphoma with mediastinal involvement who were treated with

mediastinal/mantle radiation and have a resting HR \geq 80 bpm.

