APPENDIX B Drug Diary

Study Participant Self-Administration Study Drug Diary Dana-Farber/Harvard Cancer Center

--

Participant Identifier: _____
Protocol # _____
Study MD _____ Phone _____

STUDY DRUG INSTRUCTIONS:

Study Drug: Ivabradine

How Much: a) 2.5 milligrams,
b) 5 milligrams, OR
c) 7.5 milligrams

How Often: Twice daily

When: With breakfast and with dinner

SPECIAL INSTRUCTIONS:

- i) do not consume grapefruit, grapefruit juice, or any other form of grapefruit
- ii) do not consume starfruit
- iii) do not consume pomegranate, pomegranate juice or any other form of pomegranate
- iv) Store drug at room temperature and keep drug in provided pill bottle
- v) a dose should be considered missed if it has not been taken within 6 hours prior to the next scheduled dose. If you miss a dose or vomit after taking the medication, please make a note of this in your drug diary. Take your next dose at your regularly schedule time
- vi) if you experience any side effects, please note this in your drug diary. If these side effects interfere with your ability to carry out your daily activities, please contact the study staff.
- vii) please keep drug in provided pill bottle
- viii) bring any unused drug, your pill bottle, and this diary to your next clinic visit
- ix) do not crush, chew, or dissolve drug in water
- x) do not skip drug on days where you come to see your doctor
- xi) please update this diary daily

OTHER MEDICATIONS TAKEN

If you take a daily medication or supplement (prescribed or otherwise), please use one line per drug and indicate the start and stop dates under the "Date(s) Taken" section (i.e., 6/2/09 - 6/5/09).

Drug Name	Dose	Dates Taken	Reason Taken

Study Participant Initials _____

Date _____

FOR STUDY TEAM USE ONLY	
Staff Initials:	
Date Dispensed:	Date Returned:
# pills/caps/tabs dispensed:	# pills/caps/tabs returned:

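### The primary analysis leaves out both pre-randomisation EKG heart rates as covariates, and no stated analysis uses the 24-hour Holters: precision is lost, but the comparison stays valid and adequately powered

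*Combined protocol and SAP*

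**What the plan says.** - **Primary outcome (13.5).** "We will calculate the change in resting HR (from EKGs) from baseline to 6 weeks for each patient in the study". The model is ANCOVA, or the Quade test if the data are not normal. The only adjustment terms listed there and in 13.3 are beta-blocker use and autonomic-testing group.
- **EKG schedule (5.3.3).** "All patients will have a standard 12 lead EKG performed at the screening, baseline, 2 week and 6 week visits". Two of these readings precede randomisation.
- **Use of those two readings.** The screening EKG serves entry (5.2.1: "Obtain an EKG to make sure that patients meet eligibility criteria"; also 3.1.7). The baseline EKG repeats the 80 bpm check before randomisation (5.2.2) and then supplies the starting value of the change score. The screening heart rate has no stated use in analysis.
- **Holter (5.3.3).** "All patients will have a 24 hour ambulatory Holter monitor placed at the baseline and 6 week visits". The Section 10 calendar agrees. No endpoint in 11.3 and no analysis in 13.3 to 13.7 names a Holter variable.
- **Heart rate variability.** Section 11.3 lists it among the exploratory endpoints ("heart rate variability, cardiovagal CASS and adrenergic CASS from baseline to 6 weeks"). Section 5.3.3 describes it within the autonomic laboratory tests given to 30 patients. Section 13.6 specifies an analysis for the two CASS scores only.

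**The concern.** A change score from one EKG carries the noise of that one reading in full. Adjusting for pre-randomisation heart rate removes part of that noise, and averaging two readings removes more. Both readings exist for every randomised patient, because both are entry requirements, so the covariate should have no missing values.

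The second gap is one of specification. Patients wear two 24-hour monitors for which the plan states no analysis. If a Holter analysis is devised after unblinding, it will be post hoc.

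What is at stake is the width of the interval around the primary estimate and the standing of any Holter result.

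**Working it through.** **1. The plan's own power.** Section 13.1 gives a difference of 10.9 bpm, SD 10.5 bpm and 27 per arm. Section 13.5 gives a two-sided 0.05 level. I read 10.5 as the SD of the change.

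SE = 10.5 × √(2/27) = 2.858. Noncentrality = 10.9 / 2.858 = 3.81 on 52 df. Power is 96.3% by noncentral t and 96.8% by the normal approximation. The stated 95% is reproduced. The 95% half-width is 2.007 × 2.858 = 5.7 bpm.

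**2. Model for the covariates.** The documents give no within-patient variance or correlation, so these inputs are assumptions: between-person SD 8-9, within-person SD 4-7, drift SD over six weeks 5, and mean heart rate before selection 75-85 bpm.

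Let T be the patient's underlying rate. Screening S = T + e1, baseline B = T + e2, week 6 F = T + drift + e3, and M = (S + B)/2. Simulated patients are kept only if S and B are both at least 80. Residual variances are:

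- planned: Var(F − B)
- ANCOVA on single baseline: Var(F) × (1 − r²), r between F and B
- ANCOVA on the two-EKG mean: Var(F) × (1 − r²), r between F and M
- change score with M as its only heart-rate covariate: Var(F − B) × (1 − r²), r between F − B and M

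| Unselected mean / between SD / within SD | SD of planned change | Single-baseline ANCOVA vs planned | Two-EKG-mean ANCOVA vs planned | Two-EKG mean vs single baseline | Change score + M only vs planned |
|---|---|---|---|---|---|
| 75 / 8 / 4 | 7.3 | −4.5% | −10.6% | −6.4% | −0.4% |
| 80 / 9 / 7 | 10.5 | −10.3% | −16.1% | −6.4% | −1.8% |
| 85 / 8 / 7 | 10.6 | −12.7% | −18.3% | −6.5% | −2.7% |
| Range over 18 settings | 7.3-10.6 | −4 to −13% | −11 to −18% | −5 to −9% | 0 to −3% |

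The settings with within-person SD 7 give a change SD close to the plan's 10.5. There the fall against the planned score is 14-18%.

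**3. Why the form of the model matters.** Subtracting B from the outcome is harmless if B is itself a covariate, because only its coefficient shifts. The change score with B and S as two separate covariates therefore has the same residual as F on B and S. Since the two readings have exchangeable error here, that matches F on M; the simulated values agree to three decimals. If M is the only heart-rate covariate beside F − B, the model cannot separate e2 from e1, and much of the baseline noise stays in the residual. That version is 4-11% worse than ANCOVA on the single baseline.

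**4. Effect on the primary result** (percentage cut applied to SD 10.5, 27 per arm).

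- 11% cut: SD = 10.5 × √0.89 = 9.91; power 97.8%; half-width 5.4 bpm.
- 18% cut: SD = 10.5 × √0.82 = 9.51; power 98.5%; half-width 5.2 bpm.

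In patients, 27 per arm then does the work of 27/0.89 = 30 to 27/0.82 = 33 per arm.

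**5. Holter.** The documents give no variance for Holter heart rate and no correlation with EKG heart rate, so no gain can be computed.

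**The case against.** The strongest reply is that the trial does not need the gain. Power is already about 96%, this is a pilot, and most of the improvement comes from ordinary baseline adjustment. The screening EKG adds 5-9% of variance, or about 2.5-4.6% of interval width. All of that stands, and it sets the weight of the point. It does not remove the point. The SD comes from a heart-failure trial, and the change costs nothing. If 10.5 were instead the SD at a single visit, with an assumed within-patient correlation of 0.3, the change SD would be 10.5 × √(2 × 0.7) = 12.4 and power about 90%.

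A reader might infer four stronger things that the documents do not support.

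- **That the 80 bpm entry rule biases the comparison.** It selects high readings in both arms alike. The screening reading is gated too, so averaging reduces noise but does not undo the selection.
- **That the week-6 Holter records washout,** because the diary says "bring any unused drug, your pill bottle, and this diary to your next clinic visit". That line applies to every visit, including week 2, and does not tell patients to stop. Section 5.1 rules out dose holds on assessment days, and 5.3.3 places the Holter before drug ends. The calendar says week-6 tests "should be completed prior to termination of study drug". The diary also tells patients not to omit doses on visit days.
- **That the variability endpoint has half the sample it could have.** The plan places it in a laboratory battery limited to 30 patients for cost. A Holter-derived measure would be a different endpoint.
- **That Holter heart rate could replace or be averaged into the primary.** A 24-hour mean is not resting EKG heart rate.

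**Conclusion.** The point holds as a matter of efficiency and specification. The planned model omits two pre-randomisation heart rates held for every patient, and the Holters have no stated analysis. The primary comparison remains unbiased and, on the plan's inputs, adequately powered.

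The direction of the gain is secure. Its size, about 11-18% of residual variance and a half-width 0.3-0.5 bpm narrower, rests on the assumed variances in the working and on reading 10.5 bpm as the SD of change. The Holter part rests on the text alone and carries no figure.

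**What to change.** 1. **Section 13.5.** Analyse week-6 EKG heart rate by ANCOVA, with the mean of the screening and baseline EKG heart rates and the two stratification factors as covariates. Alternatively, keep the change score and enter baseline and screening heart rate as two separate covariates. Do not add the two-EKG mean alone to the change score. Under randomisation the treatment effect estimated is the same difference in heart-rate change that 11.3 names. State the matching covariates for the Quade branch.
2. **Section 13.5 or 13.6.** Name change in 24-hour mean Holter heart rate, adjusted for its own baseline value and the two strata, as supportive of the EKG primary and not a replacement.
3. **Optional.** Add Holter-derived heart rate variability in all patients as a separate exploratory measure, not interchangeable with the laboratory measure. State an analysis for the laboratory measure too.
4. **Appendix B.** Clarify that the drug-return line is consistent with the calendar's requirement for week-6 tests.

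Items 1 and 2 need no new visit, test or patient; the cost is text and analysis time, assuming 24-hour mean heart rate can be read from the scheduled recordings. All should be written in before unblinding.

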2.3 Other Agents

Ivabradine is a hyperpolarization-activated cyclic nucleotide-gated channel blocker that reduces the spontaneous pacemaker activity of the cardiac sinus node by selectively inhibiting the I_f current, resulting in heart rate reduction with no effect on ventricular repolarization and myocardial contractility. Ivabradine causes a dose-dependent reduction in heart rate. The size of the effect is dependent on the baseline heart rate (i.e., greater reduction occurs in subjects with higher baseline heart rate). At recommended doses (2.5-7.5 mg twice daily), HR reduction is approximately 10 bpm at rest and during exercise. Analysis of HR reduction vs. dose indicates a plateau effect at doses > 20 mg twice daily. Ivabradine increases the uncorrected QT interval with HR slowing but does not cause rate-corrected prolongation of QT.

Following oral administration, peak levels of ivabradine are reached in approximately 1 hour under fasting conditions. The oral bioavailability is about 40% due to first pass metabolism in

the gut and liver. Food delays absorption by 1 hour and increases plasma exposure by 20-40%. Therefore, it is recommended that ivabradine be taken with food. It is about 70% plasma-protein bound with a volume of distribution of approximately 100 L at steady state.

Ivabradine is metabolized by the liver and intestines via CYP3A4 mediated oxidation. The major metabolite is the N-desmethylated derivative (S 18982), which is equipotent to ivabradine and circulates at concentrations approximately 40% that of ivabradine. The N-desmethylated derivative is also metabolized by CYP3A4. Ivabradine plasma levels decline with a distribution half-life of 2 hours and an effective half-life of approximately 6 hours. The total clearance of ivabradine is 24 L/h, and renal clearance is approximately 4.2 L/h, with ~ 4% of an oral dose excreted unchanged in urine. The excretion of metabolites occurs to a similar extent via feces and urine. No adjustment in dose is required for hepatic or renal dysfunction. Due to the fact that it is metabolized by CYP3A4, concomitant administration of others drugs that are metabolized by CYP3A4, such as ketoconazole, diltiazem, verapamil, grapefruit juice and St. John's wart is not recommended.

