2.5 Correlative Studies Background: N/A

3. PARTICIPANT SELECTION

3.1 Eligibility Criteria

- 3.1.1 Survivors of mediastinal lymphoma (either Non-Hodgkin's Lymphoma or Hodgkin's Lymphoma) with no active malignancy
- 3.1.2 Prior mediastinal or mantle radiation ≥ 5 years prior to enrollment in the study
- 3.1.3 Age 18-80 years. Patients < 18 years will be excluded since ivabradine has not previously been studied in children. Patients > 80 years will be excluded since patients have to be able to perform a treadmill exercise stress test as part of this study.
- 3.1.4 ECOG performance status: N/A
- 3.1.5 Life expectancy: N/A
- 3.1.6 Participants must have normal organ function as defined below:
 - AST(SGOT)/ALT(SGPT) $\leq 2.5 \times$ institutional upper limit of normal
 - creatinine clearance ≥ 15 mL/min/1.73 m² for participants with creatinine levels above institutional normal.
- 3.1.7 Normal sinus rhythm with resting heart rate ≥ 80 bpm on screening EKG
- 3.1.8 Based on findings in animals, ivabradine may cause fetal harm when administered to a pregnant woman. For this reason, women of child-bearing potential must agree to use highly effective contraception (as described in Appendix A) prior to study entry and for at least 2 weeks after the last dose of ivabradine. Should a woman become pregnant or suspect she is pregnant while she or her partner is participating in this study, she should inform her treating physician immediately.
- 3.1.9 Ability to understand and the willingness to sign a written informed consent document.

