All patients (n=60) will complete the SF-36 health survey at baseline and at 6 weeks. The SF-36 questionnaire consists of eight subsections; physical functioning, social role functioning, physical role functioning, emotional role functioning, mental health, vitality, bodily pain, and general health perceptions. For each section, item scores are coded from 0 (worst health status) to 100 (best health status). Total scores are also obtained for two main domains: a physical component -consisting of physical function, role physical, bodily pain, and general health subscales- and a mental component -consisting of role emotional, social functioning, mental health, and vitality. SF-36 has been used to assess quality of life in several cancer populations. Change in SF-36 scores from baseline to 6 weeks will be calculated for each patient. An ANCOVA model (for normally distributed data) adjusting for the stratification factors (beta blocking agents [Yes, No], autonomic function testing [Yes, No]) or Quade test adjusting for the stratification factor (beta blocking agents [Yes, No], autonomic function testing [Yes, No]) (for non-normally distributed data) will be implemented to compare the change in quality of life with ivabradine versus placebo. A p value $<$ 0.05 using a two-sided test will be considered statistically significant.

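### The change-score analyses of resting HR, exercise duration and SF-36 do not adjust for the outcome's baseline value; adding it is a low-priority efficiency gain, not the repair of an error

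*Combined protocol and SAP*

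**What the plan says.** Section 13.5 takes each patient's change in EKG resting HR from baseline to 6 weeks and compares arms with "An ANCOVA model (for normally distributed data) adjusting for the stratification factors". The factors are beta-blocker use (yes/no) and autonomic function testing (yes/no). A Quade test with the same two factors replaces the ANCOVA for non-normal data. Section 13.3 sets this as the general rule: the model "will be implemented to compare the change in various endpoint with ivabradine versus placebo".

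Section 13.6 repeats it for the secondary endpoint ("will be implemented to compare the change in exercise duration with ivabradine versus placebo") and for quality of life ("Change in SF-36 scores from baseline to 6 weeks will be calculated for each patient"). The one further covariate named anywhere is the change in resting HR, in a repeat of the exercise analysis. The baseline value of the outcome is not listed in any of these models.

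The baseline values exist. Section 5.3.3 and the Section 10 calendar schedule the EKG, treadmill test and SF-36 at baseline and week 6, and Section 10 adds "Baseline evaluations/tests are to be conducted within 1 week prior to start of protocol therapy".

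Two other statements bear on the HR slope. Section 2.3 says of ivabradine that "greater reduction occurs in subjects with higher baseline heart rate". Eligibility (3.1.7) requires "resting heart rate ≥ 80 bpm on screening EKG". Section 5.2.2 begins "Obtain an EKG to make sure that patients are in sinus rhythm" and sets the same 80 bpm threshold again at the baseline visit, before randomisation. Section 13.2 counts a baseline HR under 80 among the losses it allows for.

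**The concern.** An analysis of change without baseline as a covariate fixes the slope of the week-6 value on the baseline value at 1. If the true slope differs from 1, baseline still explains part of the change. That part stays in the residual variance, and part of any chance baseline difference between arms stays in the estimate. Adding the baseline value lets the data set the slope.

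For HR, a slope below 1 is plausible. Patients must be at or above 80 bpm on two EKGs. Where a patient's HR varies between readings, those who pass tend to be lower later, whichever arm they are in. Truncation on baseline alone would not lower the slope; within-patient variability does. The Section 2.3 statement describes a drug effect, so it supports a lower slope in the ivabradine arm only.

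With 27 analysed patients per arm, what is at stake is the width of the interval around the HR effect and its sensitivity to baseline imbalance. These are one matter: the effect of imbalance is the same variance seen in a particular trial, not a second harm.

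**Working it through.** **1. The plan's own figures (Section 13.1).** Two-sided t test, alpha 0.05, 27 per arm.
- HR: 10.9/10.5 bpm gives 96.3% power, against 95% stated.
- Exercise duration: 34% − 12% = 22 points with SD 24% gives 91.1% (52 df), or 91.0% on the 50 df of the planned model, against 90% stated.

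Both reproduce, and neither calculation uses a baseline covariate.

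**2. HR formulas.** Let sB be the baseline SD, b the slope of week 6 on baseline, and 10.5 bpm the SD of change.
- Share of variance removed = sB²(1 − b)² / 10.5².
- Half-width unadjusted = t(50) × 10.5 × √(2/27) = 2.0086 × 10.5 × 0.2722 = 5.74 bpm.
- Half-width adjusted = t(49) × 10.5 × √(1 − share) × √(2/27) × √(1 + 1/49), with t(49) = 2.0096.
- Shift in the unadjusted estimate from a 2-SE baseline imbalance = 2 × sB × √(2/27) × (1 − b).

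**3. Baseline SD (assumed).** A normal distribution with mean 75 and SD 10, cut at 80, has SD 5.2 bpm. Other assumed sources give 4.0 (75/8), 6.0 (80/10) and 8.2 (85/12).

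**4. HR results at sB = 5.2.**

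| Slope b | Variance removed | Half-width (bpm) | Shift at 2-SE imbalance (bpm) |
|---|---|---|---|
| 0.3 | 12.0% | 5.44 | 1.98 |
| 0.5 | 6.1% | 5.62 | 1.42 |
| 0.7 | 2.2% | 5.74 | 0.85 |
| 0.8 | 1.0% | 5.77 | 0.57 |
| 1.0 | 0% | 5.80 | 0 |

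Break-even: 1 − 1/[(t49/t50)² × (1 + 1/49)] = 2.1% of variance, which is a slope of about 0.71. Above that, adjustment costs slightly more than it returns. A wider baseline SD of 8 bpm would give 28.4% and 4.91 bpm at slope 0.3, but needs a source near mean 85 and SD 12.

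**5. Both EKG thresholds.** Simulation with source 75/10, HR at or above 80 on both screening and baseline readings, no drug effect, and assumed reliability of a single reading:

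| Reliability | Baseline SD (bpm) | Slope | Removed, as share of 10.5² |
|---|---|---|---|
| 0.5 | 5.6 | 0.41 | 10.1% |
| 0.6 | 5.6 | 0.49 | 7.6% |
| 0.7 | 5.5 | 0.58 | 4.9% |
| 0.8 | 5.4 | 0.68 | 2.7% |

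So about 3% to 10%.

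**6. Exercise duration.** Assumptions: SD of change 0.24 × 9.2 = 2.208 min and baseline SD s = 2.9 min, using the Section 2.1 mean and SD for irradiated patients with elevated resting HR. Let the week-6 SD be k × s. Then b = (s² + k²s² − 2.208²)/(2s²), and the share removed is s²(1 − b)²/2.208².

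| k | Slope b | Variance removed | Power |
|---|---|---|---|
| 1.00 | 0.71 | 14.5% | 94.2% |
| 1.12 | 0.84 | 4.6% | 91.7% |
| 1.23 | 0.97 | 0.2% | 90.5% |
| 1.34 | 1.11 | 2.0% | 91.0% |

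Unadjusted power is 91.0%. The last three rows let the spread grow with the mean, by the 12% and 34% improvements and their midpoint.

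**7. SF-36.** The documents give no SD, effect or correlation, so no calculation is possible.

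**The case against.** The strongest reply is that a prespecified change-score comparison in a randomised pilot is a legitimate choice. Primary power is already about 96%, so adjustment will hardly alter the chance of a significant HR result. At a baseline SD of 5.2 bpm, the best case in the table narrows the half-width by 0.30 bpm against a 10.9 bpm target, and slopes above 0.71 make it slightly wider. All of this stands, and it is why the point carries low weight.

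It is also fair that Section 2.3 lends little support to a low slope in both arms. In 20,000 simulated trials with slopes of 0.5 on ivabradine and 0.7 on placebo, the SD of the estimate was 2.86 bpm unadjusted and 2.83 adjusted, about 1%. The case for HR therefore rests mainly on regression to the mean.

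Scope is a further objection. The exercise gain may be nil and the SF-36 gain is unknown. That stands as to size. Including them keeps one model across endpoints at negligible cost.

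A reader might infer that the planned test is biased, invalid or underpowered. The documents do not support this: allocation is randomised, the change score estimates the same contrast, and the power figures reproduce without a covariate. A reader might also apply the equal-variance rule, under which correlations of 0.5 to 0.7 would remove 25% to 15% of the variance. For HR that does not fit, because the 80 bpm thresholds narrow the baseline spread but not the week-6 spread.

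What survives on the other side is cost. The data are already collected, the worst case is trivial, and naming the covariate in advance removes the choice between adjusted and unadjusted results after unblinding.

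**Conclusion.** The omission is real for all three endpoints, and its consequence is limited to efficiency. The planned analysis may stand as it is without any conclusion becoming invalid.

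For HR the likely return is modest: roughly 3% to 10% of variance if both EKG thresholds and a single-reading reliability of 0.5 to 0.8 are assumed, and 12% to 0% across slopes of 0.3 to 1.0 at a baseline SD of 5.2 bpm. For exercise duration it runs from a trivial loss to a gain of about 3 percentage points of power, depending on whether the spread grows with the mean.

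The omission itself is certain. Every size rests on an assumed slope, SD, reliability or variance ratio and should be read as a range.

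**What to change.** In Sections 13.3, 13.5 and 13.6, add the baseline value of the outcome as a continuous covariate in the ANCOVA, and ranked baseline in the Quade version, for resting HR, exercise duration and each SF-36 score. Keep both stratification factors. Make the change before unblinding.

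The cost is one sentence in each section and no new data. Statistically it uses one residual degree of freedom (50 to 49 with 54 patients). It inflates the standard error by √(1 + 1/49), about 1%, on average, and by √(1 + 4/52), about 4%, in a trial with a 2-SE baseline imbalance; if the true slope is 1, nothing offsets this. The worst cases in the tables are a half-width of 5.80 instead of 5.74 bpm for HR and power of 90.5% instead of 91.0% for exercise duration.
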